#### 9.4.3 Time to Death (from first Infusion of SBC-102)

Time to Death (months) = [(Date of Death - Date of First SBC-102 Infusion + 1)/365.25]\*12;

This derived variable will be used in the calculation of Kaplan-Meier estimate of median survival since first dose of SBC-102.

#### 9.4.4 Time to Peak ADA Titer

Time to Peak Titer (Weeks) = (Date of Peak ADA Titer - Date of First SBC-102 Infusion + 1)/7;

Alexion Pharmaceuticals LAL-CL08

This derived variable will be used in the calculation of Kaplan-Meier estimate of median time to peak ADA titer (if calculable), and probability of "no titer detected" at selected time points.

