4.4 Exclusion Criteria

A subject who meets any of the following criteria will be ineligible to participate in the study:

- Clinically important concurrent disease or co-morbidities which, in the opinion of the Investigator and Sponsor, would interfere with study participation, including, but not restricted to:
 - a. Additional severe congenital abnormality
 - b. Presence of severe infection that requires treatment with parenteral anti-infective treatment within the past 14 days
 - c. Previous history of circulatory collapse requiring inotropic support for more than 48 hours

Page 30 of 66

- d. Congestive heart failure
- e. Acute or chronic renal failure
- f. Other extenuating circumstances such as life-threatening under nutrition or rapidly progressive liver disease
- 2. Subject will be > 8 months of age at the time of first dosing.
- 3. Subject has received an investigational medicinal product other than sebelipase alfa within 14 days prior to the first dose of sebelipase alfa in this study.
- 4. Myeloablative preparation, or other systemic pre-transplant conditioning, for hematopoietic stem cell or liver transplantation.
- 5. Previous hematopoietic stem cell or liver transplant.
- 6. Known hypersensitivity to eggs.

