8.8.2 Clinical Laboratory Tests

Observed measurements and changes from baseline to each study timepoint in clinical laboratory data will be summarized. Clinically significant abnormal values will be listed. Frequencies of abnormal values relative to the laboratory normal range and clinically significant abnormal values will be tabulated for each study timepoint. Shift tables may also be provided.

Time to ADA positivity, median and peak antibody titer, and time to peak antibody titer; antibody titer values will be tabulated at each study visit using summary statistics appropriate to the data.

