# 5. **DEFINITIONS**

#### 5.1. Safety

#### 5.1.1. **Primary Endpoint(s)**

This study is designed primarily to evaluate the safety and tolerability of IV infusion of SBC-102. Safety and tolerability will be assessed based on:

- Incidence of treatment-emergent adverse events (TEAEs)
- Serious adverse events (SAEs), and infusion-associated reactions (IARs)
- Changes from baseline through trial completion in clinical laboratory tests
- Changes in vital signs during and post-infusion, relative to pre-infusion values
- Physical examination finding
- Use of concomitant medications/therapies
- Characterization of ADAs, including ADA positivity rate, time to ADA positivity, median and peak ADA titer, and time to peak ADA titer

Given the potential for ADAs to alter the safety profile of sebelipase alfa, the impact of ADAs on safety endpoints may be explored, sample size permitting. Further characterization of ADAs, including inhibitory and/or neutralizing ADAs and measurement of specific ADA subtypes (e.g., IgE), may also be performed.

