#### 7.2.2.2. AEs, SAEs and IARs by System Organ Class (SOC) and Preferred Term (PT)

The frequencies of TEAEs, SAEs, IARs and percentage of patients with events will be tabulated by PT within SOC. Patients are counted once in each SOC and PT. Percentages will be based on the total number of patients in the specific analysis population. SOCs will be listed in order of frequency of occurrence.

Frequencies will also be presented by the classifications of severity and causality. In addition, frequency of AEs, SAEs, and IARs will be presented for time periods spanning the entire course of treatment with SBC-102: from the start of dosing with SBC-102 in this study to 3 months after the first dose; >3 to 6 months; >6 to 12 months; >12 to

Alexion Pharmaceuticals LAL-CL08

18 months; >18 to 24 months; and >24 months. The incidence of AEs leading to study discontinuation will also be summarized.

Summaries of adverse events will be summarized by anti-drug antibody (ADA) status. Subjects who developed ADA vs subjects who did not develop ADA. For subjects who developed ADA, only those AEs reported on or after the first time ADA were identified will be summarized. The number of subjects experiencing any TEAE will be presented overall and by relationship to study drug, with AE specific details presented by SOC and PT, also by relationship to study drug. This table will also be generated for all TESAEs and for all IARs.

Detailed listings of patients who experience AEs, SAEs and IARs will be presented. Detailed listings will include severity and relationship to treatment, seriousness, as well as action taken regarding study treatment, other action taken, and patient outcome. A separate listing of patients who discontinued from the study due to a treatment-emergent AE will also be provided.

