#### 7.2.8. Antidrug Antibody (ADA) Titer

A subject is considered as having been ADA positive if both the initial titer and a confirmatory titer were positive at that visit.

ADA data will be summarized and include both the number and percentage of subjects who become ADA-positive and positive to neutralizing antibodies.

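### SAP 9.4.4 reads the probability of 'no titer detected' from time to peak ADA titer, so infants between first positive and peak count as having no titer; time to ADA positivity is never derived

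*SAP*

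**What the plan says.** SAP 5.1.1 places the ADA measures among the primary safety endpoints: "Characterization of ADAs, including ADA positivity rate, time to ADA positivity, median and peak ADA titer, and time to peak ADA titer". Protocol 8.8.2 names the same quantities: "Time to ADA positivity, median and peak antibody titer, and time to peak antibody titer". In both, time to positivity and time to peak are separate items.

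SAP 9.4.4 defines "Time to Peak Titer (Weeks) = (Date of Peak ADA Titer - Date of First SBC-102 Infusion + 1)/7". It then says that this variable supplies the "Kaplan-Meier estimate of median time to peak ADA titer (if calculable), and probability of 'no titer detected' at selected time points".

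SAP 7.2.8 defines positivity visit by visit: "A subject is considered as having been ADA positive if both the initial titer and a confirmatory titer were positive at that visit". The analysis planned there consists of counts and percentages: "ADA data will be summarized and include both the number and percentage of subjects who become ADA-positive and positive to neutralizing antibodies". SAP 7.2.2.2 needs the date of first positivity for another purpose: "For subjects who developed ADA, only those AEs reported on or after the first time ADA were identified will be summarized".

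SAP 9.4 derives time to death (from birth and from first infusion), time to peak titer and time to transfusion-free hemoglobin normalization. It does not derive time to ADA positivity. SAP 4.1, which lists departures from the protocol, does not say that this endpoint was dropped.

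**The concern.** A Kaplan-Meier curve estimates the probability that its event has not yet happened. Here the event is dated at the peak titer, so the curve describes not yet having peaked. That differs from having no detected titer for every infant whose titer rises after the first positive sample. From first positive to peak, such an infant has a confirmed titer but is reported under 'no titer detected'.

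The variable that would carry the label correctly, time to first confirmed positive, does not exist in the SAP, and nothing says how infants who never become positive are censored. The peak is also only the highest titer seen while the infant is followed, so death or early withdrawal can cut it short.

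What is at stake is how one safety output is read. Protocol 1.5.2 notes that antibodies to approved enzyme replacement therapies may go with altered response or more infusion reactions. A figure that makes infants look antibody-free for longer than they are would mislead on timing.

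**Working it through.** The documents give no ADA rate or timing, so there is no planned figure to reproduce. The check is of the rule itself, followed by its size under stated assumptions.

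**The rule applied to one infant (hypothetical).** First confirmed positive on day 56 after first infusion, peak on day 168.
- SAP 9.4.4 variable: (168 + 1)/7 = 24.1 weeks.
- Same form applied to the first positive date: (56 + 1)/7 = 8.1 weeks.
- For 24.1 − 8.1 = 16 weeks this infant has a detected titer but is counted as having none.

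**Direction.** The peak cannot come before the first positive, so P(not yet peaked by t) ≥ P(not yet positive by t) at every t. The two are equal when first positive and peak coincide for every infant who becomes positive, or when t is after every peak.

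**Weight of one infant.** SAP 9.3 expects no more than 10 treated infants. With 10 and no dropout before t, Kaplan-Meier equals the simple proportion, so each infant between first positive and peak adds 1/10 = 0.10. One infant positive at Week 8 and peaking at Week 60 gives 0.90 from first positive and 1.00 from the SAP variable throughout that interval. If 2, 4 or 6 of 10 become positive at Week 8 and peak at Week 24, the Week 12 value should be 0.80, 0.60 or 0.40. The SAP variable gives 1.00 each time.

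**A wider assumed range.** Let p be the share who become positive (0.3, 0.6, 0.9). First positive is uniform on Weeks 4 to 24, the lag to peak is uniform on 0 to L weeks, and follow-up is complete.

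Overstatement at week w = p × [F_first(w) − F_peak(w)]

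- F_first(12) = (12 − 4)/20 = 0.40; F_first = 1 from Week 24.
- F_peak(w) for w up to 24 (and L at least 20) = (w − 4)²/(2 × 20 × L).
- L = 24: F_peak(12) = 64/960 = 0.067; F_peak(24) = 400/960 = 0.417; F_peak(48) = 1.
- L = 72: F_peak(12) = 64/2880 = 0.022; F_peak(24) = 400/2880 = 0.139; F_peak(48) = (44² − 24²)/2880 = 1360/2880 = 0.472; F_peak(96) = 1.

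| Lag to peak | Week | F_first − F_peak | p = 0.3 | p = 0.6 | p = 0.9 |
|---|---|---|---|---|---|
| 0 | any | 0 | 0 | 0 | 0 |
| 0–24 weeks | 12 | 0.333 | 0.10 | 0.20 | 0.30 |
| 0–24 weeks | 24 | 0.583 | 0.18 | 0.35 | 0.53 |
| 0–24 weeks | 48 | 0 | 0 | 0 | 0 |
| 0–72 weeks | 12 | 0.378 | 0.11 | 0.23 | 0.34 |
| 0–72 weeks | 24 | 0.861 | 0.26 | 0.52 | 0.78 |
| 0–72 weeks | 48 | 0.528 | 0.16 | 0.32 | 0.48 |
| 0–72 weeks | 96 | 0 | 0 | 0 | 0 |

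For p = 0.6 and lag 0–72 weeks, the correct values at Weeks 12, 24, 48 and 96 are 0.76, 0.40, 0.40 and 0.40. The SAP variable gives 0.987, 0.917, 0.717 and 0.400.

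**The case against.** **The estimate need not be biased one way.** The inequality holds for the underlying probabilities and for complete follow-up. With early censoring a Kaplan-Meier estimate can go the other way. Suppose 3 of 10 infants become positive at Week 8 and peak at Week 48, 4 never-positive infants are censored between those weeks, and 3 never-positive infants are followed to the end. After Week 48 the peak curve has 3 events among 6 at risk and reads 0.50, while the first-positive curve reads 7/10 = 0.70. This stands as a limit on the sizes above, which assume no dropout. It does not rescue the SAP variable, which in that example is wrong in both directions: 1.00 against 0.70 before Week 48, then 0.50 against 0.70.

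**The label could mean status at a visit.** An infant who reverts to negative would then again have no titer detected, which a first-positive curve does not show. But a probability taken from a Kaplan-Meier time-to-event variable is not a visit-level prevalence, and protocol 8.8.2 already tabulates titers by visit for that purpose.

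**The missing derivation can be inferred.** SAP 7.2.8, SAP 7.2.2.2 and the form of the neighbouring formulas point to it, and SAP 9.4.2, 9.4.3 and 9.4.5 state no censoring rule either. That shows the repair is easy. The SAP still tells the programmer which variable to use for 'no titer detected', and it is the wrong one.

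**The output is minor.** It is one clause in an appendix. Nothing is formally tested, and listings show each infant's data. This stands, and it bounds the importance of the point. The assumed rates and lags above have no support in the documents and should not set its weight.

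**Conclusion.** The rule is wrong as written. SAP 9.4.4 attaches 'no titer detected' to a variable whose event is the peak, no other section corrects it, and a listed endpoint has no derivation. The error is zero if every first positive is also the peak. Otherwise, with 10 infants and no earlier dropout, it is 10 percentage points for each infant between the two dates. Larger figures depend on the assumed positivity rate and lag. The damage is confined to this descriptive output: the positivity rate in SAP 7.2.8 does not use the peak, and the adverse event, serious adverse event and infusion-reaction tables in SAP 7.2.2.2 use the first positive date. It should be corrected before the analysis is run, but it does not threaten the trial's main safety tables.

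**What to change.** Add a derivation to SAP 9.4: time to first confirmed ADA positive (weeks) = (date of first confirmed positive after first infusion − date of first infusion + 1)/7, with confirmation as in SAP 7.2.8. Then:

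- Censor infants who never become positive at their last ADA sample.
- Use this variable for the Kaplan-Meier median time to positivity and for 'no titer detected', labelled as no titer detected up to that time.
- Show beside the curve how many infants died or left before any positive sample.
- Report infants already positive before the first infusion, including on the pre-dose sample, on a separate line. Leave them out of the curve and label its denominator accordingly. Protocol 4.4 bars only an "investigational medicinal product other than sebelipase alfa within 14 days prior to the first dose", so earlier exposure to the study drug is possible, although no document says such an infant would enrol.
- Keep time to peak for its own summary: median and range among ADA-positive infants, with a note that the peak is the highest titer observed and may be truncated by death or withdrawal.

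The cost is SAP wording and one derived variable. SAP 7.2.2.2 already needs the first positive date, so no new data are required.

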#### 9.4.5 Time to Transfusion-Free Hemoglobin Normalization

Time to Transfusion-Free Hemoglobin (Weeks) = (Date of First Assessment in 4 week period where conditions for TFHN are satisfied\* - Date of First SBC-102 Infusion + 1)/7;

\*See Section 7.3.1.3 for details.

#### 9.4.6 Body Mass Index (BMI)

BMI is calculated as:

```
BMI = body weight (Kg) / [\text{Height (m)}]^2
```

BMI is expressed in Kg/m^2

#### 9.4.7 Derivation of Study Day

The date and time of first study drug infusion is the reference day for deriving study day, with study day calculated as follows:

- for measurements on or after first study drug infusion, study day is:
  - $\circ$  collection date first study infusion date + 1.
- for measurements prior to first study drug infusion, study day is:
  - $\circ$  collection date first infusion date -1.

#### 9.4.8 Definition of Baseline Values and Change from Baseline

#### 9.4.8.1 Baseline

Baseline is defined as the last available assessment prior to the start of the first infusion of sebelipase alpha. If any Baseline laboratory analyte is evaluated at both the local and the central laboratory, then the central laboratory results will be used for analysis.

#### 9.4.8.2 Change from Baseline

Change from baseline will be calculated as:

Change of Baseline = Assessment Value - Baseline Assessment Value.

Change from pre-infusion, at a given visit, will be calculated as the infusion or post-infusion value minus the preinfusion value.

#### 9.4.8.3 Percent Change from Baseline

Percent change from baseline will be calculated as:

Percent Change of Baseline = [(Assessment Value – Baseline Assessment Value)/(Baseline Assessment Value)]\*100 and rounded to 2 decimal places.

Similarly, the percent change from pre-infusion, at a given visit, will be calculated as the infusion or post-infusion value minus the pre-infusion value, all divided by the pre-infusion value.

#### 9.4.9 Adverse Events

The analysis of Adverse Events is described in detail in Section 7.2.2.

#### 9.4.9.1 Treatment-emergent Adverse Events (TEAEs)

Treatment-emergent AEs (TEAEs) are events with start dates and start times on or after the date and time of the first study drug infusion (SBC-102). All other AEs with complete start dates and start times are considered Pre-Treatment Adverse Events (PTAEs).

Percentages are based on the total number of treated patients.

#### 9.4.9.2 Missing AE Dates

If the start date or time of an AE is partially or completely missing and the end (stop) date or time of the AE does not indicate that it occurred prior to the first dose or the end date or time does not indicate that it occurred prior to the first dose, then treatment-emergence will be determined as follows:

- If the start year is after the year of the first study drug dose, then the AE is treatment-emergent; else,
- If the start year is the same as the year of the first study drug dose and
  - the start month is missing, then the AE is treatment emergent; else if
  - the start month is present and is the same or after the month of the first study drug dose, then the AE is treatment-emergent; else.
- If the start date is completely missing, then the AE is treatment-emergent.
- If the start date is the same as the date of the first study drug dose and start time is missing, then the AE is treatment-emergent.

To be able to calculate time from first dose to AE, the following are rules to input AE start dates:

Imputation Rules for Partial Dates (D = day, M = month, Y = year)			
Parameter	Missing	Additional Conditions	Imputation
Start date for AEs	D	M and Y same as M and Y of first dose of study drug	Date of first dose of study drug
		M and/or Y not same as date of first dose of study drug	First day of month
	D and M	Y same as Y of first dose of study drug	Date of first dose of study drug
		Y is after Y of first dose	Set to Jan 1st
	D, M, Y	None - date is completely missing	Date of first dose of study drug

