7.3 Recording of Adverse Events

At each contact with the subject (and the subject's parent or legal guardian), the Investigator must seek information on AEs by specific questioning and, as appropriate, by examination. Information on all AEs should be recorded immediately in the source documentation and in the eCRF. All clearly related signs, symptoms, and abnormal diagnostic procedures results should be recorded under one diagnosis.

AEs will be recorded from the time of signing of the informed consent until completion of the last scheduled visit, i.e., the follow-up visit. Adverse events occurring after signing the informed consent but prior to the first dose of study medication will only be recorded if assessed as related to protocol procedures or requirements. Any AEs remaining unresolved at the completion of the last visit should be recorded as ongoing. Ongoing AEs/SAEs should continue to be followed up for the period specified in Section 7.2.2 but without further recording in the eCRF. However, follow-up information on SAEs must be reported to the Sponsor or designee as described in Section 7.4.1. Any SAE that occurs after the study period and is considered to be related to the study treatment or study participation should be recorded and reported immediately.

Any AE that occurs within 24 hours of the infusion will be recorded by time and date, AEs occurring 24 hours after the infusion will be recorded by date only. The date and time, or the date when the AE started and stopped, as well as the intensity, seriousness, action taken with regard to the study treatment, causality assessment and outcome of the event will be recorded for each AE.

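### The missing-date rule for adverse events ignores a known start day, so a date-only event that began before first dose in the same month is classed as treatment-emergent

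*SAP*

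**What the plan says.** SAP 7.2.2 divides adverse events into those between consent and the start of SBC-102 (pre-treatment) and those on or after first dose (treatment-emergent). It sets no clock-time condition. Pre-treatment events are only listed; treatment-emergent events are listed and tabulated.

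SAP 9.4.9.1 defines TEAEs as "events with start dates and start times on or after the date and time of the first study drug infusion". Its pre-treatment category is narrower than a simple remainder: "All other AEs with complete start dates and start times are considered Pre-Treatment Adverse Events (PTAEs".

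SAP 9.4.9.2 deals with incomplete data. It is triggered "If the start date or time of an AE is partially or completely missing", provided that the end "date or time of the AE does not indicate that it occurred prior to the first dose". Its same-year branch makes the event treatment-emergent if "the start month is present and is the same or after the month of the first study drug dose". A later bullet covers a missing time on the day of dosing: "If the start date is the same as the date of the first study drug dose and start time is missing", the event is treatment-emergent.

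On recording, Protocol 7.3 asks for date and time within 24 hours of an infusion, whereas "AEs occurring 24 hours after the infusion will be recorded by date only". Events after consent but "prior to the first dose of study medication will only be recorded if assessed as related to protocol procedures or requirements".

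**The concern.** A missing clock time alone is enough to send an event into 9.4.9.2. Once there, an event with a fully known date is judged by year and month. No branch lets a known day place the event before dosing. The only way out is an end date or time showing that the event was over before first dose, and an event still ongoing at first dose has none.

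SAP 9.4.9.1 does not correct this, because its pre-treatment category needs both a complete date and a complete time. A date-only event from an earlier month of the same year meets neither the treatment-emergent branches of 9.4.9.2 nor the pre-treatment definition of 9.4.9.1, so it has no class at all.

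TEAE incidence is the first-listed primary safety measure in SAP 5.1.1, and the class decides whether an event is tabulated or only listed. The plan would be counting as treatment-emergent some events that its own data show began before treatment.

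**Working it through.** The plan states no figure on this point, so there is none to reproduce.

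**1. The rule applied to examples.** The dates are assumed, in a non-leap year. Each event has a complete start date, no time, and no end shown before first dose.

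| First dose | Start | SAP 9.4.9.2 as written | Comparison of dates |
|---|---|---|---|
| 20 March | 5 March (15 days before) | treatment-emergent | pre-treatment |
| 20 March | 19 March (1 day before) | treatment-emergent | pre-treatment |
| 20 March | 28 February (20 days before) | no branch met | pre-treatment |
| 2 March | 27 February (3 days before) | no branch met | pre-treatment |
| 20 March | 20 March | treatment-emergent | treatment-emergent |
| 20 March | 1 April (12 days after) | treatment-emergent | treatment-emergent |

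An onset 15 days before dosing is treatment-emergent and one 3 days before is not. The class depends on where the month boundary falls, not on the time before dosing.

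**2. Share misclassed.** Inputs: the screening window of up to 21 days (Protocol 4.8), and two assumptions that are not in the documents, namely first-dose dates spread evenly over the calendar and onsets spread evenly over the window. Four calendar years contain 48 months and 1,461 days. For an onset j days before dosing, with j shorter than any month, exactly j first-dose days in each month put the onset in the previous month. Hence

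share in same month at lag j = 1 − 48j/1461.

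Averaged over lags 1 to k, the mean lag is (k + 1)/2:

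- k = 7: 1 − 48 × 4/1461 = 0.869
- k = 14: 1 − 48 × 7.5/1461 = 0.754
- k = 21: 1 − 48 × 11/1461 = 0.639

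Day-by-day enumeration over four years gives the same values. The share is about 64% over the full window and rises towards 87% if onsets cluster in the last week.

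**3. Effect on a table.** SAP 9.3 expects no more than 10 treated patients. One child wrongly counted in a row, with no other event in that row, adds 1/10 = 10 percentage points. The number of such events cannot be derived from the documents.

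**4. Time periods.** The imputation table in 9.4.9.2 fills in only a missing day, month or year, so a known pre-dose date is left alone. The periods in SAP 7.2.2.2 begin at the start of dosing. A misclassed event would therefore enter the overall TEAE tables but fit none of the period columns.

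**5. Side effects of comparing dates.** An event starting on or after the first-dose date is either in a later year, or in the same year and the same or a later month. Both rules call it treatment-emergent. Enumeration over 0 to 1,099 days after dosing found no disagreement.

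**The case against.** The best defence is intent. The bullet on first-dose-day events does compare full dates, and it is the only one that mentions a missing time. It would be redundant if the month branch were meant to govern complete dates. The section title and the heading of the imputation table also point to missing or partial dates. Moreover, SAP 7.2.2 plainly makes an event before SBC-102 pre-treatment. On this view 9.4.9.2 is loosely worded, and the plan has not chosen to misclassify anything.

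That is a fair account of what was probably meant, and it rules out saying that the section never looks at the day. But the bullet only adds events that the month branch already includes. Nothing confines the month branch to a missing day, and the trigger expressly includes a missing time. A programmer following the text gets the wrong class.

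The objection on scale also stands. An event must be procedure-related, lack a time, fall in the same month and not be shown to have ended before dosing. The documents give no rate for any of these. Listings still show every event, and the error overstates TEAEs rather than hiding harm.

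A reader might infer that this is the normal route for pre-dose events. Protocol 7.3 makes date-only recording plausible for them, but its date-only sentence concerns events after an infusion, and nothing says how pre-dose times are captured.

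**Conclusion.** The wording of SAP 9.4.9.2 conflicts with SAP 7.2.2 and 9.4.9.1 for one defined group: events with a complete start date before first dose in the same calendar month, no start time, and no end shown before first dose. These are classed as treatment-emergent, always in the direction of inflating the TEAE tables. Date-only events from an earlier month of the same year are left unclassed.

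Under the even-spread assumptions, about 64% of date-only, not-ended events in the screening window would be misclassed. The base count is unknown and likely to be small. The point still deserves correction, because it affects a primary safety classification in a study of at most about 10 children.

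A reader might infer that the column from first dose to 3 months would be inflated. The documents do not support this: the column starts at dosing and the event keeps its pre-dose date. What follows instead is a possible mismatch between the overall and by-period tables.

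**What to change.** In SAP 9.4.9.2, apply the year and month rules only when the start day is missing. When the start date is complete and only the time is missing, compare dates: before the date of first dose is pre-treatment; on or after it is treatment-emergent.

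Reword both sentences of SAP 9.4.9.1 to match. A TEAE starts on or after the date and time of the first infusion or, if the time is missing, on or after the date of the first infusion. An event with a complete start date that does not meet this is a PTAE.

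Dropping the start-time condition from the pre-treatment sentence alone would not do. The TEAE sentence would still require a time, so post-dose events recorded by date only, as Protocol 7.3 prescribes beyond 24 hours after an infusion, would fall into the pre-treatment remainder.

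The cost is a few sentences in the SAP. Data collection is unchanged, and no event starting on or after the first-dose date loses its treatment-emergent class through a missing time.
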